## 8. Study procedures:

Procedure/Activity	Frequency
Patient randomization	Randomization will occur in clusters of one week. All patients in the same week will receive the same therapy (ketamine or placebo), with the choice being determined by a pre-generated random sequence.
intraoperative ketamine bolus (0.5mg/kg) vs placebo followed by continuous infusion 5 mcg/kg/min	once
postoperative ketamine infusion (2.5 mcg/kg/min, up to 100kg max) vs placebo for 48 hours	once
electronic medical record chart review	for data capture and statistical review

Data will be abstracted from the EMR. Some data will be obtained through the Research Derivative. The Research Derivative is a database of clinical and related data derived from the Medical Center's clinical systems and restructured for research. Data is repurposed from VU's enterprise data warehouse, which includes data from StarPanel, VPIMS, and ORMIS (Operating Room Management Information System), EPIC, Medipac, and HEO among others. The medical record number and other person identifiers are preserved within the database. Data types include reimbursement codes, clinical notes and documentation, nursing records, medication data, laboratory data, encounter and visit data, among others. Output may include structured data points, such as ICD 9 codes or encounter dates, semi-structured data such as laboratory tests and results, or unstructured data such as physician progress reports. The database is maintained by the Office of Research Informatics under the direction of [name].

**Due to a national shortage of ketamine, study enrollment was paused on April 3rd, 2023 and then resumed on September 18th, 2023.**

## **9. Risks:**

Ketamine is an analgesic that has been proven to reduce opioid consumption after surgery. It also has a role in reducing the development of chronic pain. Compared to opioids, ketamine has a favorable side-effect profile, including the maintenance of respiratory and cardiovascular stability. Ketamine does not act at the mu opioid receptor, and therefore is not associated with nausea, itching, constipation, and tolerance.

We have been safely utilizing perioperative ketamine VUMC for several years as part of our enhanced recovery pathways.

Ketamine is a controlled substance and is highly regulated, recorded, and tracked. Patients are evaluated daily at the bedside by our Preoperative Medicine Service, and patients are screened for side effects of ketamine on daily rounds. Nurses are trained to immediately report any suspicion of an adverse ketamine reaction to a member of our team, who is in-house 24/7.

**Adverse reactions to ketamine:** Adverse reactions and allergies to ketamine are routinely reviewed by both medical providers and pharmacy personnel prior to ordering and administering the drug. Ketamine is a controlled substance and is highly regulated, recorded, and tracked. Patients are evaluated daily at the bedside by our Preoperative Medicine Service, and patients are screened for side effects of ketamine on daily rounds. Nurses are trained to immediately report any suspicion of an adverse ketamine reaction to a member of our team, who is in-house 24/7.

**Selection of patients:** Only patients receiving care through our enhanced recovery pathway (which includes the standard administration of ketamine) will be eligible for participation.

**Ineffective pain control:** Patients with breakthrough pain will receive routine treatment guided by our preoperative protocols and discretion of medical providers.

**Breach of confidentiality:** The investigators have access to the medical data as part of their job standing. All database work will be performed on VUMC approved and password protected servers that are physically located in the VUMC computing environment and maintained by VUMC security standards. Only the PI and KSP will have access to study specific data.

## **10. Reporting of adverse events or unanticipated problems involving risk to participants or others:**

Quality controls will include regular data verification and protocol compliance checks. Protocol adherence will be monitored by the PI throughout the study. Events determined by the PI to be unanticipated problems involving risks to subjects will be reported by the PI to the IRB as per VHRPP Policies and Procedures

If any breach of confidential patient material were to occur, the Institutional Review Board at Vanderbilt University Medical Center would be immediately contacted.

## **11. Study withdrawal/discontinuation:**

Patients and their medical providers will be blinded to their randomization arm. Provisions for breaking the blind include medical emergencies, adverse medication reactions, and participant or medical provider request. Patients can request to be withdrawn from the study at any time. Should a patient choose to withdraw from continued study drug administration, outcomes will continue to be collected from the EMR unless the patient indicates they do not want their data collected.

## **12. Statistical considerations including sample size justification (power analysis) and statistical analysis plan (optional at this stage for investigators not versed in statistical methodology):**

This study is a cluster randomized, pragmatic clinical trial. Initial analysis will use descriptive statistics and data visualizations to both identify and address spurious values, and to characterize the study cohort. Characteristics will be grouped by study arm, but we do not plan to compare the study arms with statistical tests.

The primary outcome is length of stay, measured in days. It is expected that length of stay is a skewed distribution, and so non-parametric methods are preferred. However, it

is not possible to consider the clustering or baseline covariates using a Wilcoxon test. Therefore, a proportional odds regression model will be used. Clustering will be taken into account using a mixed-effects model. If there are patients included twice because they underwent two elective major abdominal surgeries, patient will also be included as a random effect. The model will include baseline characteristics such as age, BMI, history of substance use (smoking status and opioid status if available), and type of surgical procedure. The common odds ratio from the model will be estimated; this quantity can be interpreted similar to the concordance probability and is robust to the proportional odds assumption. We will also report the model-assisted estimands of mean and median length of stay. Bootstrapping will be used to generate appropriate confidence intervals.

We will use an intention to treat analysis and all participants who are randomized will be included in the statistical analysis and analyzed according to group assignment. Participants will be removed from the analysis if their provider deems the patient ineligible prior to study drug administration. If a participant or provider withdraws the participant from the study following study drug administration, the participant will receive care at the provider's discretion, but will remain in the statistical analysis.

The secondary outcomes will be explored in a similar way. The proportional odds model will be used to evaluate differences in opioid use in the hospital. Occurrence of events will be reported as rates with confidence intervals. Logistic regression will be used to compare the odds of events between groups.

In all statistical modeling, emphasis will be placed on effect sizes over p-values. In addition, continuous variables will be modelled flexibly using cubic splines. Differential treatment effects will be explored by examining the interaction between the treatment indicator and the putative subgrouping variable. We will explicitly test for effects of treatment by sex. As before, continuous variables will not be categorized, and the interaction will be with the continuous variable. Subgroup analyses will not occur in reporting the main results of this trial unless there is evidence of a differential treatment effect.

To determine how long this trial will need to run to have sufficient power to detect a meaningful difference, we assumed 85% power, a type I error rate of 5%, and a 10% reduction in LOS. We estimated the within period correlation from preliminary data concerning the length of stay for major abdominal surgeries to be about 0.014. Given these assumptions, about 1514 patients would need to be included overall. If the effect size were bigger, say 20%, then 370 patients would be required. An increase in sample size is necessary to accommodate for the two post-randomization exclusions that are pre-specified. We expect ~30 participants to be impacted by these post-randomization exclusions and will therefore increase the sample size by 30 to account for this (n=1544). Given surgical volumes, we expect 20 patients to be enrolled each week, and for the trial to last approximately 18 months. The current accrual rate has been more aligned with ~15 patients enrolled each week. Accordingly, the trial is anticipated to last approximately 26 months.

### **13. Privacy/confidentiality issues:**

Study team members will access the EMR in order to collect data for our primary and secondary outcomes. All team members have been trained in proper care of PHI. After enrollment with PHI, participants will be assigned a corresponding number to de-identification purposes, and they key will be secured in a database separate from the study data collected. All database work will be performed on VUMC approved and password protected servers that are physically located in the VUMC computing environment and maintained by VUMC security standards. Only the PI and KSP will have access to study specific data.

### **14. Follow-up and record retention details:**

Identifiers will be maintained only through the duration of the study and subsequent publication, after which the information will be destroyed.

**Statistical Analysis Plan for the Effect and Contribution of a Perioperative Ketamine Infusion in an
Established Enhanced Recovery Pathway**
[name], [name], and [name]

Version 1.0
September 6, 2023
NCT04625283
IRB #200210

Principal Investigator: [name] [name]

Key Study Personnel:

[name] [name]
[name]
[name], BS
[name]
[name], MS
[name], MS
[name]
[name], MS
[name]
[name]
[name], MS
[name]
[name]
[name], NP
[name], MSc
[name], BS, CCRP
[name], BA

Introduction

This document describes the statistical analysis plan (SAP) for a cluster randomized, pragmatic clinical trial studying the effect of ketamine within a pre-established enhanced recovery program on patients presenting for elective major abdominal surgery. Each week is considered a cluster with each cluster being randomly assigned to either the control or intervention condition.

Opioid consumption during the perioperative period is associated with adverse outcomes. In efforts to decrease opioid exposure after surgery, medical providers at Vanderbilt University Medical Center (VUMC) employ a multi-modal approach to pain control, which includes strategic combinations of non-narcotic pain medications and regional nerve blocks. Evidence is clear that combinations of non-narcotic pain medications with different mechanisms of actions are synergistically effective. What is not known, however, is the individual contribution of each medication to the overall efficacy of the regimen. This trial intends to explore the contribution of ketamine and hypothesizes patients randomized to receive ketamine will have a significant reduction in length of stay (LOS), following anesthesia start, compared to those receiving placebo.

Study Population

Adult patients presenting on a weekday for an elective major inpatient abdominal surgery at VUMC will be screened for eligibility. Indications for exclusion will be noted if they meet criteria specified in the study protocol. Two post-randomization exclusions have been prespecified for this study. First, a patient directly transferred from the operating room to the Intensive Care Unit (ICU) with an endotracheal tube placed will not be included. The rationale is that these patients are exposed to both a sedative and narcotic infusion for the duration of their intubation, which would confound the ability to determine analgesic efficacy and/or side effects from the study drug. Furthermore, Enhanced Recovery After Surgery (ERAS) protocols are not followed in the ICU, and therefore there would be significant deviations from study protocol. Importantly, we aim to study ketamine's effects within ERAS principles for specifically elective surgeries. A transfer to the ICU while intubated reflects the occurrence of a major, unintended, and unanticipated intraoperative event for these elective procedures. The focus for that patient is no longer expedited recovery, but rather life-sustaining measures. Second, abortion of planned surgical procedure will qualify as a post-randomization exclusion. These patients do not undergo the intended surgical experience, will have different care pathways and goals, and are often discharged prior to 48 hours (length of time for the intervention). This exclusion will be defined as the patient being discharged home within 23 hours of anesthesia stop time, consistent with an 'observation' status rather than 'inpatient admission' to the hospital. Manual chart review will be performed to ensure appropriate exclusion. The occurrence of these exclusions will be tracked between study arms. Eligible patients will be consented for inclusion in the trial usually on the day of their surgery; patients returning for a follow up procedure that meets inclusion criteria will be reapproached for consent and rerandomized as appropriate.

Cohort Definition for Data Analysis

Intent-to-Treat Cohort

Intent-to-treat cohort includes all participants who are eligible and did not meet exclusion criteria specified in the study protocol.

Per-Protocol Cohort

To better understand the potential efficacy of ketamine, a per protocol cohort will be analyzed which will include patients in both arms who did not have the study infusion stopped for adverse effects. The per-protocol cohort includes participants who finished the 48-hour post-operative infusion (either ketamine or placebo), as well as participants for whom the study infusion was intentionally discontinued early because the patient met appropriate recovery milestones and was preparing for discharge. However, this per-protocol cohort will exclude any patients in whom the study infusion was stopped for intolerance or side effects, including those patients who were discharged prior to 48 hours but had the post-operative study infusion stopped prior to 48 hours due to intolerances or side effects.

Treatment Arms

Randomization of treatment arms will occur in clusters of one week so that all patients in the same week will receive the same therapy (i.e., ketamine or placebo).

- A. **Intervention:** Patients will receive a weight-based (up to 100 kg max) intraoperative ketamine bolus (0.5 mg/kg) followed by continuous infusion (5 mcg/kg/min), and an additional postoperative ketamine infusion (2.5 mcg/kg/min, up to 100 kg max) for 48 hours.
- B. **Placebo:** Patients will receive an intraoperative saline bolus followed by continuous infusion of equivalent volume to study drug dosed for 5 mcg/kg/min, and an additional postoperative saline infusion for 48 hours at an equivalent volume of infusion as the intervention arm.

Outcomes

Primary Outcome

The primary outcome is the LOS in days for the placebo arm and the intervention (ketamine) arm. LOS is defined as the time between anesthesia start and the patient being discharged (patient physically leaving the hospital).

Secondary Outcomes

1. Total consumption of post-enrollment inpatient opioids in morphine milligram equivalents during the perioperative period to hospital discharge
2. The incidence of following surgical outcomes:
 - a. rapid response team calls
 - b. transfer to ICU (not including direct transfer from OR to ICU as these patients are excluded from the study) after patient has been sent to the PACU or floor
3. The incidence of the following indications or side effects requiring early cessation of the study medication, as documented by the provider at the time of discontinuing the order (from Best Practice Advisory, BPA)
 - a. Meeting milestones/preop for discharge
 - b. Mild side effects, but prefers discontinuation
 - c. Debilitating hallucinations
 - d. Debilitating dizziness
 - e. Hemodynamic instability
 - f. Other severe side effect

4. The incidence of ileus requiring gastric decompression as defined by orogastric or nasogastric tube placement in the postoperative period

Exploratory Outcomes

1. Instances of reoperation within the index encounter
2. VUMC hospital readmissions within 30 days post-discharge (not including ED visits)

Design Considerations

Randomization

Randomization will occur in clusters of one week. All patients in the same week will receive the same therapy (ketamine or placebo), with the selection being determined by a pre-generated random sequence.

Power and Sample Size

We anticipate the use of ketamine will reduce LOS following surgery start. To determine how long this trial will need to run to have sufficient power to detect a meaningful difference, we assumed 85% power, a type I error rate of 5%, and a 10% reduction in LOS. We estimated the within period correlation from preliminary data concerning the length of stay for major abdominal surgeries to be about 0.014. Given these assumptions, about 1514 patients would need to be included overall. An increase in sample size is necessary to accommodate for the two post-randomization exclusions that are pre-specified. We expect approximately 30 participants to be impacted by these post-randomization exclusions and will therefore increase the sample size by 30 to account for this exclusion (n=1544). Given surgical volumes, we expect 20 patients to be enrolled each week, and for the trial to last approximately 18 months.

Statistical Approach

Descriptive Analysis

We will describe the study cohort both overall and by treatment arm. To characterize the study sample, demographic and clinical data will be described. Categorical variables will be described using frequencies and proportions; continuous variables will be described using means and standard deviations as well as medians and interquartile ranges (IQR). Missingness will be recorded for each variable. To further assess the distribution of variables, graphical summaries will be displayed using graphs such as boxplots, dotplots, and/or histograms. No statistical testing will be performed to compare characteristics between groups. At a minimum, the following baseline variables will be described:

- Age (years)
- Sex assigned at birth (male, female, unknown)
- Race
 - Caucasian
 - African American
 - American Indian
 - Asian
 - Decline to answer
 - White

- Hispanic/Latino/a
 - None of these
 - Other
 - Unknown
- Ethnicity (Hispanic/Latino, Non-Hispanic/Not Latino, Unknown)
- Weight (kg) and height (m²), and BMI (kg/m²) will be calculated with weight and height
- Van Walraven modified Elixhauser score
- History of Smoking
- Type of Surgical Procedure (colorectal, ventral hernia, or surgical oncology – mutually exclusive categories)
- Epidural vs. truncal nerve block
- Intraoperative time, as defined by anesthesia start time to anesthesia stop time
- The last American Society of Anesthesiologists (ASA) Physical Status classification associated with the surgery (anesthesia encounter)
- Opioid exposed or naïve, as defined by the perioperative medicine initial consult note
- Known history of anxiety, as defined as any code present in the patient's chart prior to, and including the date of enrollment
- Known history of depression, as defined as any code present in the patient's chart prior to, and including the date of enrollment
- Known history of PTSD, as defined as any code present in the patient's chart prior to, and including the date of enrollment

Main Analysis

The main statistical analyses will be performed with the intent-to-treat cohort. As a part of sensitivity analyses, the per-protocol analysis will be performed with the primary outcome and the first secondary outcome defined in Secondary Outcomes section (i.e., total consumption of post-enrollment inpatient opioids in morphine milligram equivalents).

Primary analysis: A mixed-effect proportional odds model will be used to compare the primary outcome (i.e., LOS) between the intervention and placebo arms with cluster as a random effect. The model will include baseline characteristics such as age, body mass index (BMI), Van Walraven modified Elixhauser score, history of smoking, epidural vs. truncal nerve block, intraoperative time, the last ASA Physical Status classification associated with the surgery, opioid naïve status, known history of anxiety, known history of depression, and known history of PTSD. Continuous variables will be modeled using cubic splines to examine non-linear relationship. For missing covariates, if the proportion of missingness is very small, single imputation will be used as appropriate; otherwise, multiple imputation will be used.

Secondary analyses: The secondary outcomes will be analyzed with the same covariates. A mixed-effect proportional odds model will be used to evaluate difference in opioid use in the hospital between the intervention and placebo arms. For each of the binary outcomes, a mixed-effect logistic regression will be used to compare the odds of events between the two arms.

Exploratory analyses: The exploratory outcomes will be presented in tables comparing the incidences of reoperation and hospital readmission within 30 days post-discharge between two arms.

Differential Treatment Effects

Differential treatment effects will be explored by examining the interaction between the treatment indicator and each variable that potentially interacts with treatment, one variable at a time, but subgroup analysis will not be performed. The variables we consider include sex, opioid naïve status, type of surgical procedure (colorectal, ventral hernia, or surgical oncology), epidural vs. truncal nerve block, known history of depression, and known history of PTSD.

References

5. Mercadante S. Opioid Analgesics Adverse Effects: The Other Side Of The Coin. *Curr Pharm Des.* 2019;25:1-6. doi:10.2174/1381612825666190717152226.

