### **6.2 Exclusion criteria:**

- allergy or contraindication to ketamine
- unable or refused to receive a neuraxial or regional nerve block
- patient refusal
- direct transfer from operating room to ICU with endotracheal tube placed
- treating team elects to exclude the patient prior to study drug administration
- abortion of surgical procedure

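### The SAP defines the aborted-surgery exclusion by discharge home within 23 hours, not by abortion of the operation; the planned chart review probably corrects this, but its criterion is not stated (minor)

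*SAP*

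**What the plan says.** Protocol section 6.2 lists "abortion of surgical procedure" as an exclusion, with no time limit and no further definition.

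The SAP, under Study Population, makes it one of two post-randomization exclusions. Its reason is that "These patients do not undergo the intended surgical experience", that their care pathways differ, and that they often leave before the 48-hour infusion would end. It then gives the operational rule: "This exclusion will be defined as the patient being discharged home within 23 hours of anesthesia stop time". The stated basis for the cut-off is that such a stay corresponds to observation rather than inpatient status. Two safeguards follow: "Manual chart review will be performed to ensure appropriate exclusion" and "The occurrence of these exclusions will be tracked between study arms".

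Under Primary Outcome, "LOS is defined as the time between anesthesia start and the patient being discharged". Under Intent-to-Treat Cohort, the main analysis set consists of eligible participants who met none of the exclusion criteria in the protocol. Under Power and Sample Size, "We expect approximately 30 participants to be impacted by these post-randomization exclusions", a figure that covers both exclusions together.

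**The concern.** LOS equals intraoperative time (anesthesia start to stop) plus the time from anesthesia stop to discharge. For patients who go home, the 23-hour rule is therefore a cut on the primary outcome: it removes LOS below intraoperative time plus 23 hours. Whether the operation was completed does not enter.

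The rule can err in both directions. A completed operation discharged 20 hours after anesthesia stop meets the definition but not the rationale. An aborted operation discharged at 30 hours meets the rationale but not the definition. If ketamine shortens stays, as hypothesized, the first error falls more often on the ketamine arm and discards some of its fastest recoveries.

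The SAP also offers two routes to the primary cohort. An analyst who follows the intent-to-treat definition back to the protocol excludes aborted operations. One who follows the Study Population definition excludes short stays. The difference between the two cohorts depends on the outcome. The planned per-protocol analysis does not bring the removed patients back.

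**Working it through.** **1. The plan's figure.** 1514 + 30 = 1544, or 772 per arm. The 1514 cannot be reproduced forward because no standard deviation is given, so I solve back for one. Inputs from the SAP: 85% power, 5% type I error (two-sided assumed), 10% reduction, within-week correlation 0.014, 20 patients per week. The design effect is 1 + 19 × 0.014 = 1.266.
- Mean scale: CV = 0.10/(1.960 + 1.036) × √(1514/1.266/4) = 0.577, so log-SD = √ln(1 + 0.577²) = 0.54.
- Log scale: log-SD = 0.1054/2.996 × 17.29 = 0.61.

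**2. Literal rule, no rescue by chart review.** Assumptions not in the documents: lognormal LOS, placebo median 4 or 5 days, 4 hours of anesthesia. True ratio is 0.90. Cut-off = 4 + 23 = 27 h = 1.125 days.

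Removed per arm = 772 × Φ(a), with a = (ln 1.125 − ln median)/s. For s = 0.54 and median 4:
- Placebo: a = (0.118 − 1.386)/0.54 = −2.349, giving 772 × 0.00941 = 7.3.
- Ketamine (median 3.6): a = −2.154, giving 772 × 0.01562 = 12.1.

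Mean LOS of those kept = median × exp(s²/2) × Φ(s − a)/(1 − Φ(a)): 4.663 v 4.216 days, ratio 0.904.

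| log-SD | Median (days) | Removed, placebo v ketamine | Mean ratio | Common odds ratio, before → after | Power loss in points, 20/week | 15/week |
|---|---|---|---|---|---|---|
| 0.54 | 4 | 7.3 v 12.1 | 0.904 | 1.391 → 1.376 | 2.4 | 1.7 |
| 0.54 | 5 | 2.2 v 4.0 | 0.902 | 1.391 → 1.385 | 0.5 | 0.7 |
| 0.61 | 5 | 5.6 v 8.9 | 0.903 | 1.339 → 1.329 | 1.8 | 1.7 |
| 0.61 | 4 | 14.5 v 21.8 | 0.907 | 1.339 → 1.318 | 4.3 | 3.9 |

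The last row removes 36 patients, more than the 30 the plan expects for both exclusions. Odds ratios are large-sample proportional odds fits. Power losses come from 6000 simulated trials per case (78 weeks of 20, or 104 weeks of 15, the accrual rate in Protocol section 12), using a t-test on weekly mean ranks without covariates; the simulation error of a loss is at most 0.31 points. Closed-form rank, log-scale and mean-scale formulas give losses of 0.7–5.4 points, or 0.6–6.0 if anesthesia lasts 3 or 5 hours.

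**3. Share already budgeted.** These losses start from 1544 analysed, but the plan powers on 1514. On the log scale, power = Φ(0.1054/(s√(4 × 1.266/N)) − 1.96). Going from N = 1544 to 1514 gives 0.926 → 0.921 (s = 0.54) and 0.855 → 0.848 (s = 0.61), a cost of 0.5–0.7 points that the allowance covers.

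**4. Ceiling implied by the allowance.** If all 30 expected exclusions were completed fast recoveries, about 12 v 18 would go, the ratio would be 0.906 and the loss 2.4–4.6 points. But the 30 also covers intubated ICU transfers and genuine abortions. With 15 such removals: 6 v 9, ratio 0.903, loss 1.6–2.6 points.

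**5. Chart review restores every completed operation.** The arms then differ by about 1 patient and the ratio is 0.900–0.901.

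**6. Aborted cases kept.** Assume 1–2% aborted (about 15–31 of 1544) and a stay after anesthesia stop with median 18–48 h and log-SD 0.6. Then P(stay > 23 h) is 0.34–0.89, so about 5–27 patients would escape the definition, both arms together.

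**7. No treatment effect.** Removals are equal in expectation. Simulated rejection without and with the rule is 5.3% and 5.5% (log-SD 0.54), 4.8% and 4.9% (0.61), all within simulation error of 5%.

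**The case against.** The best defence is that the literal reading is not the intended one. The item being defined is abortion of the procedure. Manual review for appropriateness has little purpose if discharge time alone decides. The intent-to-treat definition refers to the protocol's criteria, under which a completed operation that leaves at 20 hours is not excluded. The cut-off has a stated basis in observation status, and the SAP's population is inpatient surgery. Patients and providers are blinded, the operating-room pharmacy tracks the allocation, and exclusions are counted by arm.

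Most of this stands, and it makes abortion-only exclusion the natural reading. What remains is that the SAP says *defined as*, not *screened by*. It states no finding that the reviewer must make, gives no route to aborted cases that stay beyond 23 hours, and does not say whether reviewers know the week's assignment or the LOS. Counting by arm would reveal an imbalance without correcting it.

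A reader might infer more: that the SAP will in fact discard ketamine's best responders, or that the rule could manufacture a benefit. The documents do not support the first, because chart review is planned. They do not support the second, because the distortion runs toward no effect and vanishes under the null. A reader might also assume shorter stays. With log-SD 0.61 and a median of 3 or 2 days, the literal rule would remove about 100 or 304 patients and cut power from about 85% to 71% or 51%. The documents give no median that would exclude this, but such counts are far from the roughly 30 exclusions planned for, so they cannot be read as what this plan would produce.

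**Conclusion.** The point holds as a minor defect of definition. The stated rule conditions the primary cohort on nearly the primary outcome, after randomization, and differs from the protocol criterion that the intent-to-treat cohort relies on. On the most natural reading of the chart review the bias is negligible. On the literal reading it is small: a true mean ratio of 0.90 becomes about 0.902–0.907, with a simulated power loss of 0.5–4.3 points, of which about 0.5–0.7 is already covered by the allowance. The direction is toward no effect and type I error is not inflated.

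These sizes depend on the lower tail of an assumed lognormal distribution, assumed medians of 4–5 days and about 4 hours of anesthesia. They illustrate the scale and are not estimates for this trial. No figure in the documents shows how many completed operations leave within 23 hours. The mismatch between the definition and the protocol criterion does not depend on any of these assumptions.

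**What to change.** Replace the 23-hour definition in the SAP with one based on the operative record: the planned operation was stopped, and neither the intended nor an alternative major abdominal procedure was completed. The second clause keeps patients whose operation was changed but who still had major surgery.

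Then state that:
- discharge within 23 hours of anesthesia stop prompts review and never excludes by itself;
- longer-staying aborted cases are flagged from the performed-procedure or case-cancellation field. Protocol section 8 names the operating-room management system as a data source; that it holds such a field is an assumption to confirm;
- reviewers judge without knowledge of week assignment and, as far as possible, of LOS;
- the exclusion applies whatever the LOS.

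Report exclusions by arm and reason, and add one LOS sensitivity analysis that retains the patients excluded as aborted.

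The cost is a few sentences in the SAP, modest extra record review because discharge time alone no longer identifies the cases, and one additional analysis of data already being collected.
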